7.2 Primary Efficacy Endpoint

7.2.1 Definition of Endpoint

[figure not shown]
The primary efficacy endpoint is the mean change of DYS measured by NRS from Baseline to Week 12 measurement. The NRS for overall endometriosis-associated pain ranges from 0 (no pain) to 10 (severe pain). Higher scores mean a worse outcome.

- The Baseline measurement will be derived from the last complete menstruation cycle (menstruation period should be ≥ 2 days) during the Screening Period prior to Day 1. It will be designated as the baseline menstrual cycle and is defined as following:

[figure not shown]
- If the first administration of IMP occurs within the menstruation but not the last day of the menstruation, the baseline menstrual cycle is defined as the interval that first day of the previous menstruation to the day before the menstruation during which the first administration of IMP occurs.

- If the first administration of IMP occurs on the last day of the menstruation, the baseline menstrual cycle is defined as the interval that begins from the first day after the end of the previous menstruation to the first dosing day.

[figure not shown]

- If the first administration of IMP does not occur during the menstruation, the baseline menstrual cycle is defined as the last menstruation period before the first dose plus the non-menstrual period prior to the last menstruation.

[figure not shown]

- The Week 6 measurement will be from a complete menstrual cycle (menstruation period should be ≥ 2 days) prior to Week 7.

[figure not shown]
- If Week 7 visit occurs during menstruation, the menstrual cycle is defined as the interval that begins from the first day after the end of the previous menstruation to the last day of the menstruation during Week 7 visit occurred. It is expected that the end of this menstruation may be days after the Week 7 visit.

- If Week 7 visit occurs outside of a menstruation period, the closest menstruation period to Week 7 visit will be identified. This menstrual period may be before or after the Week 7 visit. In either case, the menstrual cycle will begin at the end of the menstruation period immediately before the closest menstruation period to the last day of the closest menstruation period.

[figure not shown]

Or

[figure not shown]

- The Week 12 measurement: Because the Week 12 (EOT) visit may or may not occur during menstruation, the measurement of Week 12 will be defined by the following 2 approaches, depending on the scenarios. The objective of these approaches is to capture a complete menstrual cycle (menstruation period should be ≥ 2 days) and designate it as the EOT menstrual cycle.

[figure not shown]
- If EOT visit occurs during menstruation, the EOT menstrual cycle is defined as the interval that begins from the first day after the end of the previous menstruation to the last day of the menstruation during which the EOT visit occurred. It is expected that the end of this menstruation may be days after the EOT visit.

- If EOT visit occurs outside of a menstruation period, the closest menstruation period to the EOT visit will be identified. This menstrual period may be before or after the EOT visit. In either case, the EOT menstrual cycle will begin at the end of the menstruation period immediately before the closest menstruation period to the last day of the closest menstruation period.

Or

The average score is calculated by adding up the daily DYS measured by NRS during analysis window and dividing by the actual number of days with non-missing daily DYS data.

The **primary estimand** is described by the following attributes:

Treatment conditions of interest:	HMI-115 at 60,120 and 240 mg vs. placebo. Placebo treatment is the control group.
Subject population:	Women with moderate to severe endometriosis-associated pain and have surgical diagnosis
Endpoint:	Mean change (change from baseline) in DYS measured by NRS at Week 12 measurement
Population-level summary:	Differences between each HMI-115 treatment group compared with placebo in mean change (change from baseline) in DYS measured by NRS at Week 12, including least square mean (LSM) with its associated standard error (SE) and 95% CIs by using ANCOVA
Intercurrent events (ICEs) and strategies to handle ICEs:	
Premature withdrawal from study treatment due to any reasons (Hypothetical strategy)
 
At least 15% increase in average pill count of rescue analgesic medications(endometriosis-associated) compared to Baseline. (Composite strategy)

Daily use of rescue analgesic medications will be recorded by the subject in the e-Diary from Visit 2 through the Follow-up period. Protocol specific rescue analgesic medication for endometriosis-associated pain will include four equivalent NSAID (non-steroidal anti-inflammatory drugs) choices and three equivalent opioid choices. For the purposes of the

rescue analgesic analysis, the number of pills for each class of rescue analgesic (NSAID or opioid) will be considered equivalent.

Table 7.1 Analgesic Change During Treatment and Follow-Up Period

Analgesic used at Baseline	Analgesic dose status at End of Time	Responder
None	None Opioid analgesic and/or NSAID is started	Responder Non-Responder
Tier 1 (NSAID)	Dose stopped, decreases, or is stable (Dose is the same as the screening dose or increases by less than 15% of the screening dose) Dose increases by 15% or more Opioid analgesic is substituted or added	Responder Non-Responder Non-Responder
Tier 2 (Opioid analgesic)	Dose stopped, decreases, or is stable** Dose stopped and NSAID substituted (any dose) Dose decreases and NSAID added (any dose) Dose stable** and NSAID added (any dose) Dose increases by 15% or more	Responder Responder Responder Non-Responder Non-Responder
Tier 1 + Tier 2 (NSAID + opioid analgesic)	NSAID dose stops + opioid analgesic use stops, decreases, or is stable** NSAID use stops + opioid analgesic dose increases by 15% or more NSAID dose decreases + opioid analgesic use stops, decreases, or is stable** NSAID dose decreases + opioid analgesic dose increases by 15% or more NSAID dose stable** + opioid analgesic use stops, decreases, or is stable** NSAID dose stable** + opioid analgesic dose increases by 15% or more NSAID dose increases by 15% or more + opioid analgesic use stops NSAID dose increases by 15% or more + opioid analgesic dose decreases NSAID dose increases by 15% or more + opioid analgesic dose is stable** NSAID dose increases by 15% or more + opioid analgesic dose increases by 15% or more	Responder Non-Responder Responder Non-Responder Responder Non-Responder Responder Non-Responder Responder Non-Responder Non-Responder Non-Responder Non-Responder Non-Responder

* **Responder** = Defined as a subject who meets the protocol-specified pain score criteria for no increase in analgesic use.

** **Stable** = Dose is the same as the baseline dose or increases by less than 15% of the baseline dose.

The average pill count for any rescue analgesic use will be calculated by adding up the number of pills (NSAID and/or opioids) at a particular visit time frame and dividing by the actual number of days in the window with non-missing data from the corresponding menstruation cycle.

The pill count will be calculated as follows:

- Tier 1:
NSAID: 1 pill 200mg Naproxen (220mg Naproxen sodium) = 1 pill 200mg Ibuprofen
= 1 pill 25mg Diclofenac = 4 pills 50mg Celecoxib = 1 pill of NSAID use;
- Tier 2:
Opioids: the pill count for hydrocodone + acetaminophen, codeine phosphate + acetaminophen and tramadol + acetaminophen will be collected from eCOA directly.

First, rescue analgesic use should be categorized as Tier 1 or Tier 2. Then calculating the pill count in each Tier.

If the strength is not the same as the above strength, the pills count can be calculated by (actual strength per pill ÷ standard strength above) *number of pills taken in the last 24 hours for Tier 1.

Tier 1 and Tier 2 are not convertible to each other.

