9.4.4 Primary Efficacy Endpoints

The primary efficacy endpoint is the mean change of DYS measured by NRS from Baseline to Week 12.

Measurement of Baseline: The baseline measurements will be derived from the last *complete* menstruation cycle during the Screening Period prior to Day 1.It will be designated as the baseline menstrual cycle and is defined as the interval from the first day of the menstruation to the day before the first day of the next menstruation.

Measurement of Week 12: Because the Week 12 (EOT) visit may or may not occur during menstruation, the measurement of Week 12 will be defined by the following 2 approaches, depending on the scenarios. The objective of these approaches is to capture a complete menstrual cycle and designate it as the EOT menstrual cycle.

- If EOT visit occurs during menstruation, the *EOT menstrual cycle* is defined as the interval that begins from the first day after the end of the previous menstruation to the last day of the menstruation during which the EOT visit occurred. It is expected that the end of this menstruation may be days after the EOT visit.
- If EOT visit occurs outside of a menstruation period, the closest menstruation period to the EOT visit will be identified. This menstrual period may be before or after the EOT visit. In either case, the *EOT menstrual cycle* will begin at the end of the menstruation

Version 6.0 64 of 138 April 11, 2024

period *immediately before* the closest menstruation period to the last day of the closest menstruation period.

The mean change will be summarized for each treatment group with point estimate and 95% CI and will be compared for each HMI-115 treatment group to the placebo group using analysis of covariance models (ANCOVA) with treatment, the randomization stratification factor of region as the fixed effects and baseline DYS as covariate. In addition, a mixed-effect model repeated measures (MMRM) method with treatment, the randomization stratification factor of region, and visit as the main effects, and treatment-by-visit interaction will be used as a sensitivity analysis.

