- The disease/disorder being studied or expected progression, signs, or symptoms of the disease/disorder being studied, unless more severe than expected for the subject's condition.
- Medical or surgical procedure (e.g., endoscopy, appendectomy): the condition that leads to the procedure is the AE.
- Situations in which an untoward medical occurrence did not occur (social and/or convenience admission to a hospital).

Version 6.0 81 of 138 April 11, 2024

 Anticipated day-to-day fluctuations of pre-existing disease(s) or condition(s) present or detected at the start of the study that do not worsen.

Adverse Events of Special Interest (AESI)

- Adverse event of special interest (AESI) is an AE (serious or nonserious) of scientific and
 medical concern specific to the Sponsor's product or program, for which ongoing
 monitoring and notification by the Investigator to the Sponsor is required.
- AESIs may be modified during a study by protocol amendment, which will enable the Sponsor to collect additional information to better assess any potential and identified risks during the development surveillance.
- The role of the DMC in the handling of these AESIs will also be considered.
- The AESI to be defined in this study includes:
 - Galactorrhea is the spontaneous discharge of milk or a milk-like secretion from the breast in the absence of parturition or beyond six months' post-partum in a non-breastfeeding woman. The secretion may be intermittent or persistent, scant or abundant, free-flowing or expressible, and unilateral or bilateral. An inquiry and breast examination can provide important clinical findings of subjects with galactorrhea.
 - Change in menstrual cycles with oligo- or amenorrhea is defined as no bleeding or spotting in a 56- day interval.
 - Hirsutism is a condition in subjects with excessive growth of dark or coarse hair in a male-like pattern —face, chest, abdomen and back.
 - Acne involves whiteheads, blackheads or pimples that usually appears on the face, forehead, chest, upper back and shoulders.
 - Palpitations are feelings of having a fast-beating, fluttering or pounding heart, or single
 forceful or skipped beats that not caused by emotional or physical stimulus, exercise, other
 drugs or food, and cannot be relieved through rest or mental relaxation.

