12.2 Analysis Visit Window for Daily Assessment

Table 12.2: Analysis Visit Window for Scheduled Visit

Study Analysis Visit	Target Study Day	Time Interval (Study Day)	
		Start	End
Screening V1			
Screening V2			-1
Baseline		-35	-1
Week 1	Day 1	1	8
Week 3	Day 15	9	22
Week 5	Day 29	23	36
Week 7	Day 43	37	50
Week 9	Day 57	51	64
Week 11	Day 71	65	78
Week 13/EOT	Day 85	79	127
Week 25/FU	Day 169	≥128	

EOT=end of treatment; FU=follow-up.

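### The Week 12 rule takes the menstruation closest to the end-of-treatment visit with no maximum distance, so with delayed or absent menses a mistimed period can count as an observed Week 12 value

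*SAP*

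**What the plan says.** The primary endpoint is the change in dysmenorrhea (DYS) NRS from Baseline to Week 12, measured over a menstrual cycle.

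- **Week 12, SAP 7.2.1.** The aim is to "capture a complete menstrual cycle (menstruation period should be ≥ 2 days) and designate it as the EOT menstrual cycle". If the EOT visit is outside menstruation, "the closest menstruation period to the EOT visit will be identified. This menstrual period may be before or after the EOT visit". The cycle scored is the one ending with that menstruation.
- **Week 12, Protocol 9.4.4.** The rule is the same: "the closest menstruation period to the EOT visit will be identified".
- **Week 6, SAP 7.2.1.** The rule has the same form, anchored on the Week 7 visit: "the closest menstruation period to Week 7 visit will be identified. This menstrual period may be before or after the Week 7 visit". The lead sentence of that item, however, places the Week 6 cycle before Week 7.
- **Score, SAP 7.2.1.** Averaging means "adding up the daily DYS measured by NRS during analysis window and dividing by the actual number of days with non-missing daily DYS data", which gives the score.

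The only condition on the chosen menstruation is the SAP's minimum of two days. Neither document gives a maximum distance from the visit, an earliest study day, a rule for absent menses, or a bar on using one menstruation for two time points. The diagrams in SAP 7.2.1 are not available here, so this describes the text only.

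Regular cycles of 21 to 35 days are required only before Day 1 (Protocol 5.1, criterion 6). Oligo- or amenorrhea is an adverse event of special interest and "is defined as no bleeding or spotting in a 56- day interval" (Protocol 10.3.1).

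**The concern.** A closest-period rule without a limit always returns a menstruation if the diary holds one. When none occurs near Day 85, the rule does not declare Week 12 missing. It takes the nearest period, however far away, and treats its score as observed. That value then bypasses Step 2 of SAP 7.2.2, which imputes missing Week 6 and Week 12 changes, and enters the primary ANCOVA as a 12-week outcome.

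Two things are at stake. The first is the meaning of the primary endpoint for subjects whose menses become delayed or stop. The second, smaller one is the imputation model, in which the Week 6 change predicts the Week 12 change. If one period serves both, the two values are identical for that subject.

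**Working it through.** **Inputs.** Nominal visits are Day 43 (Week 7) and Day 85 (EOT), and the last dose is on Day 71. Visit windows are Day 43 ±3, and Day 85 ±2 (intensive PK) or ±4 (sparse PK). Day 1 falls on cycle days 1 to 5. All are from Protocol 1.3. The eligible cycle length of 21 to 35 days is from Protocol 5.1. Menses of 5 days is an assumption; 2 to 7 days was also run for regular cycles.

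**Selection rule.** Let a period end on day e before the visit on day v, and let the next period start on day n. The earlier period is chosen when v − e < n − v, that is, n > 2v − e. For v = 85 this means n ≥ 171 − e, with at least n − e − 1 = 170 − 2e bleed-free days.

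**Regular cycles.** With a 35-day cycle and 5-day menses, the last day of one period and the first day of the next are 31 days apart, so the nearer is at most 15 days from EOT. With 2-day menses they are 34 days apart, so at most 17. Enumerating cycles of 21 to 35 days with these visits, no period serves both Week 6 and Week 12.

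**Delayed or absent menses (nominal visits)**

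| Pattern | Distance to Day 85 | Selected as Week 12 | Also Week 6? |
|---|---|---|---|
| 26-day cycles, period Days 53-57, next Day 114 (56 bleed-free days) | 85 − 57 = 28 v 114 − 85 = 29 | Days 53-57 | Yes: 53 − 43 = 10 v 43 − 31 = 12 for Days 27-31 |
| 28-day cycles, period Days 57-61, next Day 110 (48 bleed-free days) | 24 v 25 | Days 57-61 | No |
| 28-day cycles, period Days 29-33, next Day 138 (104 bleed-free days) | 52 v 53 | Days 29-33 | Yes: 43 − 33 = 10 |
| Period Days 29-33, next Day 130 (96 bleed-free days) | 52 v 45 | Day 130 onward, 130 − 71 = 59 days after the last dose | No |
| Period Days 1-5, next Day 166 or later, or none | 80 v 81 or more | Days 1-5 | Yes |

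The shortest single gap that makes one period serve both time points is 52 days at nominal visits (period Days 55-59, next Day 112). At the window edges it is 40 days for intensive PK (visits on Days 46 and 83) and 36 days for sparse PK (Days 46 and 81).

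**Week 12 equal to Baseline.** If the first dose falls on the last day of menstruation, SAP 7.2.1 defines Baseline as the day after the previous menstruation through the first dosing day. If no menses follows, the closest menstruation to EOT is the one that ended on Day 1. Its cycle runs from the end of the previous menstruation to Day 1. Taking both starts as the same day, the intervals coincide and the change is 0.

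**Illustrative size.** The plan's figure reproduces: with 34 per group, SD 2.0 and a 1.4-point difference, 1.4 / (2.0 × √(2/34)) = 2.89, and two-sided power at 0.05 is 0.81. The rest is assumption, since no frequency is given. Suppose a fraction f of active subjects lose a share k of the effect and placebo is unaffected. The difference becomes 1.4 × (1 − f × k).

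| f | k = 0.5: difference, power | k = 1: difference, power |
|---|---|---|
| 2% | 1.386, 0.80 | 1.372, 0.80 |
| 20% | 1.26, 0.73 | 1.12, 0.62 |

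**The case against.** **Rarity.** Entry requires two regular cycles, hormonal therapy is prohibited, and Protocol Table 2-1 considers drug-induced menstrual change very unlikely. This stands. It limits how many subjects are affected but does not supply a rule for them.

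**Early-treatment scores.** A reader might infer from the 56-day event definition that such scores are a foreseen outcome. The documents do not support that. In the 56-day example the selected period is a mid-treatment one, Days 53-57. A period near Day 29 needs about 100 bleed-free days or no further menses.

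**Concealment.** A reader might infer that the plan hides the absence of a Week 12 menstruation. It does not. SAP 4.3 summarises on-study cycle length with a category above 35 days, 7.3.6 reports changes in cycle days, 8.1 tabulates events of special interest by arm, and 7.2.2 provides a by-subject DYS listing. The remaining problem is how the primary analysis treats the value.

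**Table 12.2.** A reader might take "Analysis Visit Window for Daily Assessment" (SAP 12.2), with its EOT window of Days 79 to 127, as the intended limit. SAP 7.2.1 does not cite it, and it could not serve: with regular 24-day cycles from Day 1, the closest menstruation starts on Day 73, outside that window.

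**Shared periods.** The primary ANCOVA uses only the Week 12 change, so sharing a period does not alter that subject's own outcome. This stands; the effect is confined to the imputation model and the Week 6 description. If the lead sentence on Week 6 prevails and the cycle must precede Week 7, Days 53-57 could not serve Week 6 at all.

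**Imputation.** Imputing a DYS score for a woman without menses is an estimand choice and is not shown to be less biased. This also stands and is a cost of the fix.

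**Conclusion.** The point holds as a gap in the primary endpoint definition, in both the SAP and the protocol. The written rule can score a mistimed period, or in one configuration the Baseline cycle itself, as an observed Week 12 value. It does so only when menses are delayed or absent on treatment.

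The size of any effect on the treatment contrast is unknown. The documents give no frequency of delayed menses and no evidence that it differs by arm, so no direction of bias can be claimed. The power figures above assume both the frequency and a loss confined to active arms. The conclusion also assumes that the unseen diagrams in SAP 7.2.1 set no limit that the text omits. The change should be made because the rule is wrong for identifiable patterns and the repair is cheap.

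**What to change.** Add to SAP 7.2.1:

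1. The menstruation selected for Week 12 must begin after Day 1 and within 35 days of the EOT visit, 35 days being the longest eligible cycle.
2. If none qualifies, the Week 12 measurement is missing, goes to Step 2 of 7.2.2, and is counted by arm as no menses in window.
3. If one menstruation qualifies for both Week 6 and Week 12, it is kept for Week 12 and Week 6 is set to missing.

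Record the departure from Protocol 9.4.4 in SAP Section 10, and add a sensitivity analysis under the uncapped rule. Reconcile the two Week 6 statements in the same edit.

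**Check against the examples.** The period on Days 53-57 begins 85 − 53 = 32 days before EOT and is kept for Week 12. Periods starting on Day 29 (56 days away) and Day 130 (45 days away) are excluded, as is the period around Day 1. With regular cycles the selected period starts at most 15 + 4 = 19 days from EOT with 5-day menses, so nothing changes.

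**Cost.** A few sentences, one extra table row and one extra analysis. A few subjects move from an observed but mistimed value to missing-at-random imputation, which predicts their score from menstruating subjects. SAP 7.3.2 to 7.3.5 reuse these windows, so the text should say whether the cap applies there, notably to non-menstrual pelvic pain, which can be scored without a menstruation. The Week 24 rule in 7.3.1 also has no limit and is not covered by this change.

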6.5.1 Rescue Medications

Protocol specific analgesic rescue medication for endometriosis-associated pain will include four equivalent NSAID choices and three equivalent opioid choices. The protocol-allowed analgesic rescue medications for endometriosis-associated pain are presented in Table 6–3. Investigators will prescribe a specific analgesic rescue medication for subjects at the time of Visit 2, taking into consideration the subject's preference and/or historical use of analgesics and the investigator's clinical judgement (based on the approved options).

Investigators are not to suggest or advise subjects on any modifications to their rescue medication regimen. Subjects will be instructed to contact the site if a change in their rescue analgesic medication is needed, such that appropriate adjustments can be considered. Investigators may then prescribe a different analgesic rescue medication (from each medication class if necessary) for the subject. Investigators should not prescribe more than one analgesic rescue medication from the same medication class at one time. The dosage outlined in Table 6-3 could be utilized, but all prescribed use of rescue analgesic medication should be according to appropriate clinical practice standards and the investigator's clinical judgment.

It is the investigator's discretion whether to withdraw a subject due to an analgesic issue.

Prophylactic use of protocol-specific rescue analgesic medications is not allowed. Use of any other analgesic medications for endometriosis-associated pain, including prophylactically, is not allowed from Visit 2 through the Follow-up Period.

Daily use of rescue analgesic medications taken for endometriosis-associated pain will be recorded by the subject in the e-Diary from Visit 2 through the Follow-up period including date of rescue medication use as well as the name, dosage and total number of the rescue medication within a 24-hour period. Detailed information on the rescue medication that will be sourced and provided to the subject can be found in the site operation manual. In addition, any pain medication taken for pain other than for rescue (such as treatment for toothache etc.) will be recorded in eCRF, not in the e-Diary.

Use of a prohibited medication for treatment of endometriosis-associated pain will be documented in the eCRF. If a subject continues to take analgesic(s) other than the protocol-

Version 6.0 42 of 138 April 11, 2024

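### SAP 7.2.1 gives inconsistent NSAID pill-count rules, so a subject who changes or mixes NSAID product or strength can be Responder or Non-Responder on the same record

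*SAP*

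**What the plan says.** The primary estimand in SAP 7.2.1 lists as a composite intercurrent event "At least 15% increase in average pill count of rescue analgesic medications(endometriosis-associated) compared to Baseline". SAP 7.2.2, step 1, acts on it: for a subject classed as Non-Responder under Table 7.1, a negative change from baseline in the dysmenorrhea (DYS) score at Week 6 or Week 12 is set to zero.

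SAP 7.2.1 describes how pills are counted in three places:

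- Before Table 7.1: "the number of pills for each class of rescue analgesic (NSAID or opioid) will be considered equivalent".
- After Table 7.1, on NSAIDs (Tier 1), where one naproxen 200 mg or one ibuprofen 200 mg also counts as one pill: "1 pill 25mg Diclofenac = 4 pills 50mg Celecoxib = 1 pill of NSAID use".
- For any other strength, the count is "actual strength per pill ÷ standard strength above) *number of pills taken in the last 24 hours for Tier 1".

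Opioids (Tier 2) have no strength rule: "Opioids: the pill count for hydrocodone + acetaminophen, codeine phosphate + acetaminophen and tramadol + acetaminophen will be collected from eCOA directly". The SAP adds that "Tier 1 and Tier 2 are not convertible to each other".

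Protocol Table 6-3 lists ibuprofen 200 mg, naproxen 200 mg, diclofenac 25 mg and celecoxib 50 mg. Protocol 6.5.1 lets the investigator prescribe a different rescue product when the subject asks for a change. It has the e-Diary record the name, dosage and number taken.

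**The concern.** A threshold of 15% needs a count with one value for a given intake. Here the class-equivalence sentence implies pill for pill, the NSAID line makes one celecoxib 50 mg capsule a quarter of a unit, and the strength formula, as printed, makes it a whole unit. Two programmers could each follow the text and classify the same subject differently.

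At stake is whether a recorded improvement is kept or replaced by zero. The same step is applied to DYS at Week 24, NMPP, DYSP and the Daily Impact scales (SAP 7.3). The PGIC responder analysis (SAP 9.3) uses the same 15% threshold, and the pill-count part of the rescue-use endpoint (SAP 7.3.5) reports the count itself. The sensitivity analysis in SAP 7.2.3 zeroes every Non-Responder from the same count, so it would not reveal a counting error.

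**Working it through.** **Inputs.** The 15% threshold and the counting rules are from SAP 7.2.1; product strengths are from protocol Table 6-3. Daily use is taken as constant within each cycle, so the average count equals the daily count. Change = (follow-up count − baseline count) / baseline count.

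**The plan's own figure.** Under the NSAID line, celecoxib 50 mg counts as n/4, so four capsules give 4/4 = 1 unit, as stated.

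**Step 1. Pill for pill against the NSAID line, Table 6-3 strengths only.**

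| Daily intake, baseline to follow-up | Pill for pill | NSAID line |
|---|---|---|
| Celecoxib 4 × 50 mg to ibuprofen 2 × 200 mg | 4 to 2: −50%, Responder | 4/4 = 1 to 2: +100%, Non-Responder |
| Ibuprofen 3 × 200 mg to celecoxib 4 × 50 mg | 3 to 4: +33%, Non-Responder | 3 to 1: −67%, Responder |
| Celecoxib 2 × 50 mg to 4 × 50 mg | 2 to 4: +100%, Non-Responder | 0.5 to 1: +100%, Non-Responder |

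The first two rows give opposite classifications, in both directions and far from 15%. The third shows that with the same product and strength the factor of four cancels.

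**Step 2. NSAID line against the strength formula.** This needs a strength outside Table 6-3; a 200 mg celecoxib capsule is assumed.

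- 1 × 200 mg by the formula, read literally: (200/50) × 1 = 4 units.
- 4 × 50 mg, the same 200 mg, by the NSAID line: 4/4 = 1 unit.
- 4 × 50 mg to 1 × 200 mg: 1 to 4 units, (4 − 1)/1 = +300%, Non-Responder, although the milligrams are unchanged.
- 1 × 200 mg to 8 × 50 mg: 4 to 8/4 = 2 units, −50%, Responder, although the milligrams double from 200 to 400.

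**Step 3. The same two cases under one strength-based rule.** Whether a unit is 50 mg or 200 mg of celecoxib, the first case is 0% (4 to 4, or 1 to 1) and the second is +100% (4 to 8, or 1 to 2). Within one product, the choice of unit does not matter once it is used throughout. It does matter when the product changes, as step 1 shows.

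**The case against.** The best defence is that the SAP can be read coherently. The class-equivalence sentence would be a general statement, and the later text, which introduces the calculation, would govern. The strength formula would be a first step that restates a capsule as standard-strength pills (200/50 = 4), after which the NSAID line turns four into one. On that reading the contradiction disappears. It is plausible, but the SAP states neither the precedence nor the second division. Protocol 9.4.3 and 9.4.4 do not settle it: they speak of pill or medication counts and give no conversion.

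The defence is right on several limits. Investigators are not to suggest changes to the rescue regimen and should not prescribe two products of one class at once (protocol 6.5.1), so switching may be uncommon. Step 2 of the working depends on an unlisted capsule strength.

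Three stronger readings are tempting and are not supported:

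- *Opioid escalation will go undetected.* Tier 2 tablets are counted raw, and protocol 6.5.1 leaves some room on strength, since "all prescribed use of rescue analgesic medication should be according to appropriate clinical practice standards and the investigator's clinical judgment". But Table 6-3 gives one opioid strength per product, and protocol 8.1.2 says the listed products are supplied. Starting an opioid from no rescue use, or moving up from an NSAID, is caught whatever the tablet strength. Only a change to an unlisted strength within Tier 2 is exposed.
- *The primary comparison is biased by a known amount.* One wrongly zeroed subject with an assumed change of −3 would move the mean of a 34-subject arm by 3/34 = 0.09 points. That is a shift in one arm, not in the treatment difference. The −3 is invented, no switch rate is given, and in a double-blind trial nothing shows that errors would favor one arm.
- *The whole rescue-use endpoint is wrong.* Only its pill-count component is affected; the percentage of days with rescue use does not depend on the conversion.

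**Conclusion.** The point holds as an inconsistency in the NSAID counting rules that can reverse Responder status and so decide whether a negative DYS change becomes zero. Listed strengths are enough to show it: −50% against +100% for one switch, +33% against −67% for another. The fourfold discrepancy in the strength formula also stands on a literal reading, but it depends on an unlisted celecoxib strength and disappears if a second division by four was intended.

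The conclusion is confined to subjects who change or mix NSAID product or strength between the baseline and follow-up cycles. Their number is not in the documents, so the size and direction of any bias in the treatment difference cannot be computed. The opioid gap is minor. Which celecoxib equivalence is right is not judged here; the passages have to be reconciled.

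**What to change.** In SAP 7.2.1, either make the NSAID equivalence line the only rule and remove or subordinate the class-equivalence sentence, or replace that line. Then state one milligram-per-unit figure for each NSAID and define, for every strength, units = total mg taken / mg per unit. The same celecoxib dose then always gives the same count. Use this derivation for the rescue intercurrent event, the PGIC 15% rule and the pill-count component of the rescue-use endpoint.

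For Tier 2, add one sentence on how a tablet of a strength not in Table 6-3 is counted, for example scaled to the listed strength of that product.

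The cost is SAP wording and one derivation program; no new data are needed. A few subjects may change Responder status, so the change is best made before unblinding. The documents do not show whether that point has passed: two unblinded interim analyses were planned, and this SAP refers to a special version for publication. If the data are already unblinded, disclose the rule that was programmed and report the alternative count as a sensitivity analysis.
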